9.4.3 Analysis of the Secondary Endpoint(s)

- 7) The ordinal scale will be used to estimate a proportional odds model by disease strata. The hypothesis test will perform a stratified test to evaluate whether the common odds ratio for treatment is equal to one. The distribution of severity results will be summarized by treatment arm as percentages. Efforts to minimize loss-to-follow-up will be considerable. However, small amounts of missing data may occur. In such cases, subjects without final outcome data will be excluded from the analysis. Sensitivity analyses will evaluate the impact of making different assumptions about missing observations. These analyses will be defined in the SAP.
- 8) Differences in time-to-event endpoints (e.g., time to at least a one category improvement in ordinal scale) by treatment will be summarized with Kaplan-Meier curves and 95%

confidence bounds. The same procedure will be used to compare time to at least a two-category improvement.

- 9) Change in ordinal scale at specific time points will be summarized by proportions (e.g., proportion who have a 1-, 2-, 3-, or 4-point improvement or 1-, 2-, 3-, 4-point worsening).
- 10) Duration of event (e.g., duration of mechanical ventilation) will be summarized according to median days with quartiles.
- 11) Binary data (e.g., incidence of new oxygen use) will be summarized as a percent with 95% confidence intervals. Comparisons between arms will be presented as differences in proportions with 95% confidence intervals.
- 12) Categorical data (e.g., 28-day mortality or ordinal scale by day) may be summarized according to proportions by category and/or odds ratios with confidence intervals.

Procedures for handling missing data, including informative censoring (e.g., a missing duration of oxygen use endpoint due to a death), will be described in the SAP.

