3.3.2. Recovery and Time to Recovery

The primary efficacy outcome measure is the time to recovery. Recovery will be defined as having a value of 1, 2, or 3 on the clinical status 8-point ordinal scale. The time to recovery will be defined as the elapsed time (in days) from randomization to the earliest day at which a subject

reaches recovery. Note that since clinical status assessments are recorded as defined in Section 4.3, the day that is being assessed (not necessarily the day the response is collected) will be used to determine the timing of events. For example, a subject with a score of 5 recorded on Days 1 - 3 and a score of 3 recorded on Day 4 will have a time to recovery equal to 3 days. It is also possible that a subject has a clinical status score > 3 reported for a particular day but was subsequently discharged on the same day. Such cases will be reviewed by the NIAID Medical Officer to make the determination of whether the subject should be considered recovered in analyses. Subject data to be reviewed as part of this determination will include the reported clinical status scores while hospitalized, where the subject was discharged to (e.g. private residence, rehabilitation facility, long-term care/nursing home), and any information regarding readmittance.

Any subjects that are lost to follow-up or terminated early prior to an observed recovery will be censored at the day of their last observed assessment. Subjects who complete follow-up but do not experience recovery will be censored at the day of their Day 29 visit. All deaths within Day 29 (and prior to recovery) will be considered censored at 28 days. Note that we do not expect many subjects to worsen after discharge.

However, we will evaluate whether any discharged subjects subsequently experience a worse clinical status and sensitivity analyses will be conducted accordingly. For these analyses, subjects who recover but are later re-admitted for COVID-19 will not be considered a recovery but will instead be censored at 28 days.

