3.3.3. Clinical Status at Specific Timepoints

The key secondary analyses include evaluation of the clinical status score at Day 15. For this outcome, Study Visit Day 15 is the timepoint of interest, not necessarily the actual study day. The score collected at the study visit corresponding to Day 15 will be used for this outcome. For analyses of this outcome, imputation of the clinical score may be performed following the rules described in Section 6.5.

Additional analyses are clinical status at Days 3, 5, 8, 11, 15, 22, and 29. As the with above, the scores that will be used are those collected at the study visits corresponding to those days.

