3.3.10. Time to Death

For analysis of time to death, the time to death will be defined as the elapsed time (in days) from randomization (or treatment administration for the safety analysis) to death. Any subjects that are lost to follow-up or terminated early prior to death will be censored at the day of their last observed assessment or last captured event (e.g. the end date of an adverse event). If it is learned that a subject who terminated early had subsequently died prior to Day 29, then the subject will be classified as dead. Subjects who complete follow-up will be censored at the earliest of their Day 29 visit and (actual) Day 29. Deaths that occur after Day 29 will be censored at Day 29.

Similar censoring methods will be used for the 14-day mortality analyses in that deaths that occur after Day 15 will be censored at Day 15 and subjects who are confirmed alive through Day 15 will be censored at Day 15. Subjects whose last observed assessment or last capture event (e.g. the end date of an adverse event) is prior to Day 15 will be censored at that last observed assessment/event.

3.3.11. Composite Endpoint of Death, SAEs, Severe AEs, Discontinuation of Study Product Administrations

A safety composite endpoint will be defined as the occurrence of at least one of the following through Day 29:

1. Death

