6.5. Missing Data

All attempts will be made to collect all data per protocol. Any data point that appears to be erroneous or inexplicable based on clinical judgment will be investigated as a possible outlier. If data points are identified as outliers, sensitivity analyses may be performed to examine the impact of including or excluding the outliers. Any substantive differences in these analyses will be reported.

For time to event outcomes, subjects who are lost to follow-up or terminate the study prior to Day 29 and prior to observing/experiencing the event will be censored at the time of their last observed assessment. Subjects who die prior to observing/experiencing the event will be censored at Day 29.

For the analysis of the key secondary outcome, subjects who are discharged but are subsequently re-admitted prior to Day 15 without a reported clinical score, their clinical score will be imputed at 7, which is the highest value for a hospitalized subject.

For the analyses of the secondary outcomes that involve clinical score (i.e. the key secondary outcome and time to improvement), if a subject is discharged from the hospital without a previously or concurrently reported clinical score of 1 or 2, then their clinical score at the time of discharge will be imputed as 2, which is the highest value for a non-hospitalized subject. If a subject terminates early from the study while they are hospitalized or completes the study while still hospitalized, the last observed clinical score assessment will be used as their final assessment.

For the modified version of the ordinal score described in Section 4.3, if a subject is discharged from the hospital without a previously or concurrently reported clinical score of 2 or 3, then their clinical score at the time of discharge will be imputed as 3, which is the highest value for a non-hospitalized subject.

For the analyses of the secondary outcomes described in Section 3.3, the following imputation rules will be used for subjects who are lost to follow-up, terminate early from the study, or do not have further outcome data available after discharge for any reason:

- Days of Non-invasive ventilation/high-flow oxygen:

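### For a subject who leaves the study in hospital, the SAP carries the last score to Day 15 where the protocol excludes; no missing-data sensitivity analysis is defined, and a death learned later has no stated rule.

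*SAP*

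**What the plan says.** **Protocol, Appendix B 9.4.3.** On the Day 15 proportional odds analysis: "In such cases, subjects without final outcome data will be excluded from the analysis". The next sentence is a commitment: "Sensitivity analyses will evaluate the impact of making different assumptions about missing observations". The protocol says that the SAP will define these analyses.

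**SAP 3.3.3 and 6.5.** Section 3.3.3 says of the Day 15 score that "imputation of the clinical score may be performed following the rules described in Section 6.5". Section 6.5 then states, for the key secondary outcome and time to improvement, that if a subject terminates early while hospitalized, "the last observed clinical score assessment will be used as their final assessment". Separate rules give a 2 to some discharged subjects and a 7 to some readmitted ones. Those are not in question here.

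**SAP 8.2.1 and Table 25.** The listed additions are subgroup, medication-of-interest, covariate-adjusted, interaction and modified-scale analyses. None varies the handling of missing scores. The only other sensitivity analysis in 6.5 is an optional outlier check.

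**Deaths.** For time to death, SAP 3.3.10 says that if an early terminator is learned to have died, that is, "had subsequently died prior to Day 29, then the subject will be classified as dead". For time to recovery, SAP 3.3.2 says that subjects lost to follow-up or "terminated early prior to an observed recovery will be censored at the day of their last observed assessment". The same paragraph censors all deaths within Day 29 and before recovery at 28 days. SAP 6.5 repeats both rules side by side.

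**The concern.** The protocol and SAP give different main analyses of the same endpoint, and neither document says which governs. Carrying an inpatient score to Day 15 treats leaving the study in hospital as a poor outcome. If that happens more often in one arm, the odds ratio moves, and no planned analysis would show it.

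The second gap is the missing death exception. Take a subject scored 5 who withdraws on Day 4 and is later known to have died on Day 9. That subject is dead in Table 66 and would be an 8 in the Table 33 and Table 35 shells. Read literally, the carry-forward sentence makes the same subject a 5 in Table 25. Baseline scores run from 4 to 7, so the carried value could be any of these. For time to recovery, two censoring rules fit this subject and no order is given.

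**Working it through.** **1. Texts side by side**

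| Item | Protocol App. B 9.4.3 | SAP |
|---|---|---|
| Early termination in hospital, no Day 15 score | Excluded | Last score carried (6.5) |
| Missing-data sensitivity analyses | Promised, to be defined in the SAP | None in 8.2.1 or Table 25 |
| Death learned after termination, Day 15 model | Not addressed | No exception in 6.5; shells 33 and 35 point to 8 |
| Same death, time to recovery | Deaths censored at Day 29 (9.4.2) | Two rules, no order (3.3.2, 6.5) |

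**2. Reproducing the plan's figure.** Protocol Appendix B 9.2 gives N = 12(z_α/2 + z_β)² / [λ²(1 − Σp³)], with p averaged over arms. Inputs are two-sided 5%, 85% power, odds ratio 1.75 and Scenario 1 (from death to best: 2, 1, 2, 7, 8, 10, 30, 40%). Then (z sum)² = 8.978, λ² = (ln 1.75)² = 0.3132 and Σp³ = 0.127, so N = 12 × 8.978 / (0.3132 × 0.873) = 394, against 396 stated.

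**3. Standard error at the planned size.** N = 1032 comes from SAP 5. Under no effect Σp³ = 0.0929, so SE(log OR) = 1/√[(1032/12) × 0.9071] = 0.113.

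**4. Effect of carry-forward, no true effect.** The documents give no termination rates, so these are assumed. A fraction of each arm is moved to score 5 and a proportional odds model is fitted to the expected proportions, without the severity covariate. The result depends on where those subjects would otherwise have been at Day 15:

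- *Full:* they would follow all of Scenario 1, so 70% would be out of hospital. At 5% v 2%, score 5 holds 0.95 × 7 + 5 = 11.65% of control and 0.98 × 7 + 2 = 8.86% of treated.
- *Restricted:* they would still be in hospital or dead (scores 3 to 8 in the ratio 10:8:7:2:1:2). At 5% v 2%, score 5 holds 7 − 5 × 7/30 + 5 = 10.83% and 7 − 2 × 7/30 + 2 = 8.53%.

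| Control v treated terminating | Full | Half and half | Restricted |
|---|---|---|---|
| 4% v 2% | 1.056 | 1.03 | 1.009 |
| 5% v 2% | 1.085 | 1.05 | 1.013 |
| 2% v 4% | 0.947 | 0.97 | 0.991 |
| equal | 1.00 | 1.00 | 1.00 |

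In standard errors, 5% v 2% is ln 1.085/0.113 = 0.72 (full) or ln 1.013/0.113 = 0.11 (restricted).

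**5. With a true odds ratio of 1.25.** Scenarios 1 and 5, last score 5 or 6, *full* assumption. Exclusion returns 1.25. Carry-forward gives 1.22 to 1.24 with equal termination (2% or 5% per arm). With 1% v 3% or 2% v 5% it gives 1.12 to 1.19 when the baricitinib arm loses more, and 1.30 to 1.35 when control does.

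**6. Effect of the death rule.** In the step 5 settings, scoring 25% to 100% of terminators as 8 instead of carrying the score moves the odds ratio by at most 0.03. With no true effect, moving 1% of the control arm to 5 gives 1.028; moving them to 8 gives 1.033.

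**7. Cost of exclusion.** Dropping 1% to 5% of 1032 leaves 1022 to 980 subjects. Power falls by at most about 2 points (odds ratio 1.25: 49.9% to 47.9%; 1.40: 83.7% to 81.7%).

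**The case against.** - **The protocol defers to the SAP.** Protocol 9.4.3 ends by leaving missing-data procedures to the SAP, and SAP 6.5 could be read as defining what counts as final outcome data. This has some force. But for this endpoint the protocol names a rule, and the promised sensitivity analyses are absent on either reading.
- **The manufacturer's addendum covers imputation.** SAP 2.1 presents it as a separate analysis by the manufacturer. It was not available, so it cannot be shown to meet or to fail the promise.
- **Known deaths are probably scored 8.** A reader might infer that the SAP orders a known death to be ignored at Day 15. No sentence says so. Table 33 has a row for death by the visit, and the Table 35 footnote carries 8 forward from the date of death. What stands is that the model's own rule has no exception and is not tied to those shells.
- **The primary endpoint is covered.** A reader might also infer that known deaths leave the recovery risk set early. The documents do not support that: SAP 3.3.2 and 8.1.1 apply the death rule to all deaths, and 8.1.1 explains that deaths take the worst rank. Only an explicit order of precedence is missing.
- **The case is rare.** Under Appendix B 7.1.1 and 7.2, stopping study drug does not end participation, and withdrawal of consent is recorded only when outcome follow-up is also refused. This stands and keeps the number of affected subjects low.

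**Conclusion.** The point holds as a conflict over the main rule for the key secondary outcome, an undelivered commitment to sensitivity analyses, and two unstated rules for deaths learned after early termination. The conflict and the missing analyses carry the weight.

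The shift depends on unequal termination between arms. Under no effect at 5% v 2% it lies between 1.01 and 1.09. The upper end requires that subjects who leave while in hospital would otherwise have done as well as everyone else, so 0.7 SE should not be read as the expected bias. Termination rates, the carried score and the omission of the severity covariate are assumptions; the figures show direction and scale only. The death-scoring gap is mainly one of consistency between tables. Severity: minor to moderate.

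**What to change.** 1. **SAP 6.5:** score as 8 any subject known to have died by Study Day 15, whether or not the subject terminated early, using the information that 3.3.10 already uses.
2. **SAP 6.5:** name one main rule for in-hospital early terminators. If carry-forward is kept, state that it departs from Protocol Appendix B 9.4.3.
3. **Table 25 and 8.2.1:** add the protocol's observed-case (exclusion) analysis, and one further analysis under a different, less favourable assumption, for example in-hospital terminators at 7.
4. **SAP 3.3.2:** add a sentence that the death rule takes precedence over early-termination censoring when a death before recovery and by Day 29 is known.

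The cost is SAP wording and two table rows. No new data are needed.

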Appendix B - ACTT-2: Baricitinib/Remdesivir vs Remdesivir

by the sites, but should be consistent throughout the study), and pregnancy test. Laboratory tests performed in the 48 hours prior to enrollment will be accepted for determination of eligibility.

⁴ Baseline assessments should be performed within 24 hours prior to first study product administration. Results of Day 1 (baseline) laboratory assessment do not need to be reviewed to determine if initial study product should be given.

⁵ Laboratory tests performed as part of routine clinical care in the 24 hours prior to first dose will be accepted for the baseline safety laboratory tests. Baseline may be the same as the screening laboratory tests.

⁶ Safety laboratory tests include WBC with differential, hemoglobin, platelets, creatinine, glucose, total bilirubin, ALT, AST, INR, d-dimer, and C-reactive protein (CRP). Note: D-dimer and CRP values may predict severity and support assessment of outcomes and unlike other safety laboratory values, D-dimer and CRP should not be graded.

⁷ Any laboratory tests performed as part of routine clinical care within the specified visit window can be used for safety laboratory testing. Window during the 10 days of dosing is ± 1 day.

⁸ Daily until hospital discharge or end of study, whichever comes first.

⁹ In-person visits are preferred but recognizing quarantine and other factors may limit the subject's ability to return to the site for the visit. In this case, the visit may be performed by phone. If subject is still hospitalized during the follow-up period, they should get Day 15, 22 and 29 assessments along with the daily clinical data collection.

- If still hospitalized at Day 15 and 29 or returns to the site for an in-person visit: collect clinical data, vital signs, safety laboratory tests, and research laboratory samples (OP swab and serum only) as able.
- If phone call only on Days 15 and 29 and all Day 22 visits: assess adverse events, clinical status (ordinal scale), readmission to a hospital, and mortality only.

¹⁰ Oropharyngeal swabs are preferred, but if these are not obtainable, nasopharyngeal or nasal swabs may be substituted.

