8.1.2.1 Measures of clinical support, limitations and infection control

The subject's clinical status will be captured on each study day while hospitalized through Day 29 or day after death whichever comes first. See more information about capturing death below. If a subject is discharged prior to Day 15, clinical status is collected on Day 15 and 29 if the subject returns for an in-person clinic visit or by phone if an in-person visit is not possible. Clinical status will also be captured on Day 22 during a phone visit. Clinical status is largely measured by the ordinal scale and the NEWS. Unlike the NEWS, the ordinal scale can also be evaluated over the

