3.2. Endpoints

Primary Endpoint

Time to recovery, where recovery is defined as clinical status in states 1, 2, or 3 of the 8-point ordinal scale, censored at Day 29.

- Clinical status of a subject (8-point ordinal scale) is defined below:
 - 8. Death;
 - 7. Hospitalized, on invasive mechanical ventilation or ECMO;
 - 6. Hospitalized, on non-invasive ventilation or high flow oxygen devices;
 - 5. Hospitalized, requiring supplemental oxygen;
 - 4. Hospitalized, not requiring supplemental oxygen - requiring ongoing medical care (COVID-19 related or otherwise);

3. Hospitalized, not requiring supplemental oxygen - no longer requiring ongoing medical care;
2. Not hospitalized, limitation on activities and/or requiring home oxygen;
1. Not hospitalized, no limitations on activities

Secondary Endpoints

The key secondary endpoint is clinical status (8-point ordinal scale) on Day 15.

The other secondary endpoints are:

- Ordinal outcome assessed daily while hospitalized and on Days 15, 22, and 29.
- NEWS assessed daily while hospitalized and on Days 15 and 29.
- Days of supplemental oxygen (if applicable).
- Days of non-invasive ventilation/high-flow oxygen (if applicable).
- Days of invasive mechanical ventilation/ECMO (if applicable).
- Days of hospitalization.
- Date and cause of death (if applicable).
- SAEs.
- Grade 3 and 4 adverse events
- WBC with differentials, hemoglobin, platelets, creatinine, glucose, total bilirubin, ALT, AST, INR, d-dimer, and CRP on Day 1; Days 3, 5, 8, and 11 (while hospitalized); and Days 15 and 29 (if attends in-person visit or still hospitalized).

Exploratory Endpoint

- Qualitative and quantitative polymerase chain reaction PCR for SARS-CoV-2 in OP swab on Day 1; Days 3, 5, 8, and 11 (while hospitalized); and Days 15 and 29 (if attends in-person visit or still hospitalized).
- Qualitative and quantitative PCR for SARS-CoV-2 in blood on Day 1; Days 3, 5, 8, and 11 (while hospitalized).

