3.3.8. Days of Oxygen

Oxygen days will be defined as the number of days where the clinical status score is equal to 5, 6, or 7. After discharge, the Post-Discharge Supplemental Oxygen CRF question regarding days of oxygenation (including ECMO, invasive ventilation, non-invasive ventilation, high-flow oxygen devices, and all other oxygen delivery devices) will be used. The total number of days will be the sum of all reported days, regardless of whether the days occur consecutively or in disjoint intervals. See Section 6.5 for the plan for handling subjects who do not have data through Day 29 or die prior to Day 29.

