Oxygenation, Non-invasive ventilation/high flow oxygen, Invasive Mechanical Ventilation / extracorporeal membrane oxygenation (ECMO), hospitalization and mortality will be assessed using results of the 8-point ordinal scale and post discharge eCRF questions.

Safety will be assessed by the following:

- Cumulative incidence of serious adverse events (SAEs) through 28 days of follow-up.
- Cumulative incidence of Grade 3 and 4 AEs.
- Discontinuation or temporary suspension of study product administration (for any reason)

- Changes in white cell count, absolute neutrophil count, hemoglobin, platelets, creatinine, glucose, total bilirubin, ALT, AST, and INR, d-dimer, C-reactive protein over time.

Clinical labs will be drawn on Days 1, 3, 5, 8, 11 and on Day 15 and 29 if the subject is able to return to the clinic or is still hospitalized.

Virologic efficacy is an exploratory endpoint and will be assessed by the following:

- Qualitative and quantitative PCR for SARS-CoV-2 in OP swab on Days 1; 3, 5, 8, 11 (while hospitalized); and Day 15 and 29 (if able to return to clinic or still hospitalized).
- Qualitative and quantitative PCR for SARS-CoV-2 in blood on Days 1; 3, 5, 8, 11 (while hospitalized).

To assess the impact of baricitinib on serum cytokine levels, blood samples will be assessed using a multiplex assay that is less sensitive to variability in sample integrity due to sample processing limitations during the pandemic. Cytokines to be tested may include (but not be limited to) IL-2, IL-19, IL-4, IL-10, IL-8, G-CSF, GM-CSF, MCP-1, MIP1 α , IL-7, IL-13, IL-31, IL-15, IL-6, IFN α , IFN γ and TNF α . The list of cytokines tested is subject to change as new information about the pro-inflammatory state of COVID-19 is known. Given the challenges of obtaining samples and evolving knowledge about COVID-19, these will be considered exploratory endpoints. The description of the final methodology utilized, and the assay performance characteristics will be included in the final study report.

The schedule of study procedures is provided in Section 1.2 of Appendix B of the study protocol.

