 - If the subject's clinical status scale is 6 at the last observed assessment, then the subject will be considered to be on non-invasive ventilation/high-flow oxygen through Day 29. The endpoint will be total days when assessments are available plus all imputed days following the last observed assessment.
 - If the subject is not on non-invasive ventilation/high-flow oxygen at the last observed assessment, then the subject will be considered to not be on non-invasive ventilation/high-flow oxygen for the remainder of follow-up. Thus, no additional imputed days will be added to the number of days recorded on available assessments.

- Days of ventilation/ECMO:
 - If the subject's clinical status scale is 7 at the last observed assessment, then the subject will be considered to be on ventilation/ECMO through Day 29. The endpoint will be total days when assessments are available plus all imputed days following the last observed assessment.
 - If the subject is not on ventilation/ECMO at the last observed assessment, then the subject will be considered to not be on ventilation/ECMO through Day 29. Thus, no additional imputed days will be added to the number of days recorded on available assessments.
- Days of Oxygen:
 - If the subject's clinical status score is 5, 6, or 7 at the last observed assessment, then the subject will be considered to be on oxygen through Day 29. The endpoint will be total days when assessments are available plus all imputed days following the last observed assessment.
 - If the subject is not on oxygen at the last observed assessment, then the subject will be considered to not be on oxygen through Day 29. Thus, no additional imputed days will be added to the number of days recorded on available assessments.
- Days of Hospitalization
 - If the subject is discharged and no further hospitalization data are available, then the subject will be assumed to not have been readmitted. Thus, no additional imputed days will be added to the number of days recorded on available assessments. If a subject dies while hospitalized, the number of days of hospitalization will be imputed as 28 days.

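### Post-discharge oxygen days: the phone-visit list omits the question the SAP relies on, and the SAP's fallback rules mishandle discharge and leave a score of 2 unclassified

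*SAP*

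**What the plan says.** **What is to be measured.** Days of oxygen, of non-invasive ventilation or high-flow oxygen, and of invasive ventilation or ECMO are secondary endpoints. While the subject is in hospital, SAP 3.3.6 to 3.3.8 count days by the ordinal score (6; 7; and 5, 6 or 7 respectively). For oxygen, SAP 3.3.8 continues: "After discharge, the Post-Discharge Supplemental Oxygen CRF question regarding days of oxygenation" is used. SAP 4.3 confirms that these outcomes "will be assessed using results of the 8-point ordinal scale and post discharge eCRF questions".

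**What phone contacts collect.** Footnote 9 of the ACTT-2 schedule (Protocol Appendix B, 1.2) covers Day 15 and Day 29 visits done by phone and every Day 22 visit. It instructs sites to "assess adverse events, clinical status (ordinal scale), readmission to a hospital, and mortality only". The ordinal scale is therefore part of the call; Appendix B 8.1.2.1 says the same: "Clinical status will also be captured on Day 22 during a phone visit".

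**What happens when data are missing.** The imputation rules in SAP 6.5 apply to subjects who are lost, terminate early, or "do not have further outcome data available after discharge for any reason". For oxygen, if the ordinal "score is 5, 6, or 7 at the last observed assessment, then the subject will be considered to be on oxygen through Day 29". A subject not on oxygen at that assessment gets no further days. Observed days are kept in both cases. Elsewhere in 6.5, for a subject discharged without a score of 1 or 2, "their clinical score at the time of discharge will be imputed as 2", but that sentence is limited to the key secondary outcome and time to improvement.

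**What the scores mean.** Each inpatient form after Day 1 records the worst state of the previous day (SAP 4.3). Category 2 is defined in SAP 3.2 as "Not hospitalized, limitation on activities and/or requiring home oxygen"; the version of the scale in SAP 4.3 leaves out home oxygen.

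**The concern.** The SAP relies on a day-count question that the protocol's list for phone contacts does not contain. Phone follow-up is expressly allowed for, so a site that follows footnote 9 to the letter may leave the endpoint without its post-discharge source.

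The fallback for an empty CRF then has two weak points. For a subject with no contact after discharge, it carries forward a score describing the worst moment of the day before the last form, which need not be the state in which the subject left hospital. For a subject reached by phone and scored 2, the score cannot show whether oxygen is still in use. SAP Table 42 and Figure 33 present oxygen days by arm, so errors of this kind enter a reported comparison.

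**Working it through.** **Inputs.** Maximum oxygen days: 28 (SAP 8.2.3). Inpatient form on Day j, for j of 2 or more, describes Day j-1 (SAP 4.3). Analysis set for duration: category 5, 6 or 7 at randomization (SAP 8.2.3). Rules: SAP 3.3.8 and 6.5 as above. The documents give no rate of missing post-discharge data, so the courses below are assumed illustrations.

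**The plan's own figure.** Forms on Days 2 to 29 describe Days 1 to 28, which is 28 days and agrees with SAP 8.2.3. Counting recorded scores on Days 1 to 29 would give 29.

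**Formula when the CRF is empty.** Let k be the number of inpatient days assessed. Total = (inpatient days scored 5 to 7) + (28 - k if the last observed score is 5 to 7, otherwise 0).

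**Worked courses, k = 7.** The first four have a score of 5 on all seven days; the fifth has a score of 5 on five days and 4 on the last two. True totals assume that oxygen status at home stays constant to Day 29.

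| Course after discharge | Last observed score | Days under the plan | True days |
|---|---|---|---|
| Off oxygen, no contact | 5 | 7 + 21 = 28 | 7 |
| Off oxygen, phone score 1 | 1 | 7 + 0 = 7 | 7 |
| On home oxygen, no contact | 5 | 7 + 21 = 28 | 28 |
| On home oxygen, phone score 2 | 2 | 7 + 0 = 7, if 2 is read as off oxygen | 28 |
| Off oxygen, no contact, last two inpatient days scored 4 | 4 | 5 + 0 = 5 | 5 |

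Rows 1 and 3 have identical data, and the rule cannot tell them apart. It is right for one and 21 days out for the other. A variant of row 1: oxygen on Days 1 to 6, weaned that evening, discharged on Day 7 with that day's form showing 5, then no contact. Here k = 6, so the rule gives 6 + 22 = 28 instead of 6.

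**Row 4 under either reading of 6.5.** If the phone score counts as further outcome data, 6.5 does not apply, and 3.3.8 counts only scores of 5 to 7 plus CRF days, so nothing is added. If 6.5 does apply, the answer turns on whether a 2 means on or off oxygen, which 6.5 does not say.

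**Range of the per-subject error.** With every inpatient day on oxygen, the gap is 28 - k: 25, 23, 21, 18 and 14 days for k = 3, 5, 7, 10 and 14.

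**Effect of a completed CRF.** With k = 7, a CRF entry of 0 gives 7 and an entry of 21 gives 28. Both are correct, so the problem lies only where the CRF is empty.

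**The case against.** The strongest reply is that the imputation is a fallback. The SAP names a dedicated CRF as its source, and collection detail is left to the manual of procedures, which is not available here. Oxygen requirement is among the measures recorded for the ordinal scale (Appendix B 8.1.2.1), the elements of the scale are captured separately (Appendix B 9.2), and schedule footnote 2 names oxygen requirement within clinical data collection. So it cannot be asserted that sites fail to ask. This stands as far as it goes, but it does not remove the conflict: footnote 9 restricts the call by its closing word, and a status item on a given day is not a count of days since discharge.

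Three stronger readings are tempting, and the documents do not support them.

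- A reader might infer that the missing phone question by itself produces 28-day values. It does not. The rule in 6.5 uses the last observed assessment, and a completed call supplies a new ordinal score, normally 1 or 2, that displaces an inpatient 5 (row 2). The 28-day error needs no contact at all after discharge.
- A reader might infer that a patient sent home on oxygen is given no oxygen days. With no contact, that patient is imputed as on oxygen to Day 29 (row 3). With a phone score of 2, only post-discharge days are at risk; the inpatient days are kept.
- A reader might infer a bias towards the arm that discharges earlier. The tablets are blinded, and nothing in the documents shows that loss after discharge, or an empty CRF, differs by arm.

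It is also fair that carrying the last on-oxygen status forward is a prespecified and cautious rule, that the endpoint is summarized by medians and quartiles, which a few extreme values move little, and that Table 42 and Figure 33 separate deaths. That separation does not help with a survivor whose 28 days were imputed, who stays in the survivors' row.

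**Conclusion.** The concern holds in a limited form. Footnote 9 and SAP 3.3.6 to 3.3.8 conflict on what is collected after discharge. Where the CRF is empty, SAP 6.5 as written puts a subject weaned just before discharge, and not contacted again, on oxygen through Day 29. For a later score of 2, 3.3.8 adds no days from the score and 6.5 leaves oxygen status undefined, so home-oxygen days can be missed.

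The size is up to 28 - k days per affected subject, about three weeks for a one-week stay. This assumes constant status after discharge and oxygen on every inpatient day. The number of affected subjects and any difference between arms cannot be derived from the documents. For a secondary endpoint reported by medians and quartiles the effect is likely modest, and the primary endpoint does not use these day counts. The point is still worth correcting, since following the footnote literally can lose the endpoint's stated data source.

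**What to change.** 1. Add to the phone list in Appendix B schedule footnote 9 the count of days on oxygen, non-invasive or high-flow support, and invasive ventilation or ECMO since discharge or the last contact, so that it matches the CRF in SAP 3.3.6 to 3.3.8.
2. In SAP 6.5, for a discharged subject with no later oxygen data, impute from oxygen status at discharge where it is recorded, and not from the inpatient score for the worst state of the previous day. Report the present carry-forward rule as a sensitivity analysis. Since the daily form looks back one day, confirm that some existing item gives the status at discharge itself, and state what is done where none does.
3. For a last score of 2, class oxygen status from the separately captured oxygen-requirement item, and state how days between contacts are filled when only a status is available.

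The cost is one extra question per phone call, a footnote edit, and a few lines of SAP text and programming. No visit is added.
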